## Specific Aims

The primary aim of this research is to determine the impact of different flow rates of a high-flow nasal cannula on spontaneous swallowing frequency at rest and swallowing effort and timing while swallowing.

## Introduction

High-flow nasal cannula (HFNC) is a non-invasive heated and humidified oxygen delivery device that is capable of delivering up to 60 L/min of flow. It is a relatively new modality that has been introduced as an alternative to conventional oxygen therapy in patients with chronic obstructive pulmonary disease (COPD), respiratory failure, obstructive sleep apnea (OSA), post-extubation, and status asthmaticus. The humidified gas preserves mucociliary function that prevents secretion retention and enhances patient's comfort. This feature allows prolonged use of HFNC in clinical sittings of up to 30 days.

In addition to its ability to provide adequate humidification levels, HFNC has various respiratory physiological effects. These physiological effects include: alveolar recruitment, dead space washout, and decreased airway resistance. The clinical value of the use of HFNC is not limited to its ventilation and oxygenation effects, it enables the patient to talk and is purported to permit oral feeding during oxygen therapy.

Currently, despite the fact that patients are often permitted to eat while receiving HFNC therapy, there is insufficient evidence regarding the impact of HFNC on swallow function. The uncertainty of the effect of this oxygen delivery device on swallow function arises not only from the limited number of studies, but also the contradictory results. For example, Sanuki et al. reported that increasing the flow rates of the HFNC resulted in enhanced swallow function by reducing reflex latency. Based on their findings, the researchers suggested that the use of HFNC should not affect the decision to start or resume feeding. Similarly, Lader et al. proposed that the use of high-flow nasal cannula should not delay oral alimentation. On the contrary, Ferrara et al. conducted a study in neonates and concluded that providing feeding while using Nasal Continuous Positive Airway Pressure (nCPAP) increased the risk of aspiration. These opposing outcomes support the need for further studies to obtain more definitive evidence.

### Spontaneous Swallowing Frequency:

Spontaneous swallowing is an airway protection reflex and the measurement of its frequency is considered to be a sensitive indicator of swallow function. This index can sensitively identify dysphagia and other swallowing-related disorders. Furthermore, the reduction in this index is associated with increased level of secretions and chest infections. One modality used to measure swallowing frequency is surface electromyography (sEMG), which records electric activity during swallow via an electrode placed on the skin under the chin. This non-invasive technology has been used for more than 20 years to record various aspects of swallowing physiology. In this study, sEMG will be used because of its feasibility, accuracy, and ability to detect a swallow.

### Swallowing Effort and Timing:

Swallowing effort via submental sEMG provides an objective measurement of lingual and sub-mental muscle activity during the act of swallowing. Measurements include muscle contraction amplitude and contraction timing/speed. Clinically, swallowing effort parameters have been used to document normative values in healthy individuals, as well as to document the effects of a disease on swallowing. Prior research has shown that both amplitude and timing are influenced by multiple factors including the volume and viscosity of the item (or bolus) being swallowed, and the age and gender of the person swallowing. However no study has investigated the effects of HFNC on either swallowing effort parameter.

## **Experimental Design and methods**

This is a prospective study designed to measure swallowing frequency and swallowing effort in fifty healthy adult volunteers (25 participants will be between 21 and 49 years old; and the other 25 above 50 years old). To recruit volunteer participants, an email will be sent via university internal email system to the faculty, students and employees in the departments of Respiratory Care and Speech Language Pathology. Snowball sampling (non-probability sampling) will also be utilized to recruit individuals outside of those departments. No compensation is offered to the participants. Enrolled participants are sub-categorized into two different age groups to

determine if there are any swallowing differences between the different age groups. Inclusion criteria include individuals who are older than 21 years of age and have no cognitive impairment. Exclusion criteria include individuals who are less than 21 years of age, have a history of dysphagia or disease/condition that may cause dysphagia, current use of medications that alter swallowing function, nasal obstruction, and the presence of a tracheostomy tube.

Upon meeting inclusion criteria, informed consent explaining the procedure and potential harm will be obtained and a copy will be given to the subject. Then, a unique identification code number will be assigned to protect the subject's identity.

HFNC:

The AIRVO 2 high-flow nasal cannula system (Fisher and Paykel Healthcare Limited, Panmure, Auckland, New Zealand) will be used. Nasal prongs sizes are chosen as per manufacturer recommendations. Participants will receive three levels of HFNC flow rates (30, 45, and 60 L/min) through nasal prongs. If a small-size nasal prong is used, the participant will receive 30, 45, and 50 L/min flow rates instead of 30, 45, and 60 L/min, as manufacturer recommendations state the maximum liter flow for a small-size nasal prong is 50 L/min. Oxygen concentration will be set at 21% and a temperature of 37 °C. First, individuals will be placed on the sEMG monitor. Following the application of the sEMG, each participant will sit quietly for 10 minutes, before being attached to the HFNC, so a baseline swallow frequency can be established. After the baseline swallow frequency is established, each participant will be asked to swallow 8 boluses: 2 trials of water at 2 volumes (5 and 10 mL) and 2 trials of applesauce at 2 volumes (5 and 10 mL). Participants will rest for 15 seconds after completing each swallow. This procedure will establish the participant's baseline swallowing effort measurements. Once these swallows have been completed, the participant will be placed on the HFNC. Each participant will be placed on three different flow rates (30, 45, and 60 L/min or 30, 45, and 50 L/min) in random order. The random order will be generated by an online random number tool (<https://www.randomizer.org>). The study participant will be subjected to each flow rate for 15 minutes. During the first 10 minutes, swallow frequency will be recorded. After 10 minutes at the given flow, the participant will complete the 8 aforementioned swallows. After completing all of the swallowing trials, the participant will be removed from the HFNC for a period of 10 minutes. This process will be repeated for all three

flowrates for a total of 32 boluses swallowed.

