## Subject Population

Fifty healthy adult volunteers above the age of 21 will be assessed.

Inclusion criteria:

- Age >21 y/o
- Functional cognition as determined by the participant's ability to follow verbal directions; no formal cognitive test will be administered. Anyone not able to follow 1-step directions will be withdrawn from the study.
- Eat a “general/regular consistency” diet—determined by scoring a 6 or 7 on the Functional Oral Intake Scale (FOIS).

Exclusion criteria:

- Age < 21 y/o
- Allergy to applesauce
- History of dysphagia or disease/condition that may cause dysphagia such as:
  - Achalasia
  - Diffuse spasm
  - Esophageal tumors or scar tissue
  - Esophageal rings
  - Gastroesophageal reflux disease (GERD)
  - Eosinophilic esophagitis
  - Scleroderma
  - Radiation therapy
  - Neurological disorders (multiple sclerosis, muscular dystrophy and Parkinson's disease)
  - Neurological damage (from a stroke or brain or spinal cord injury)
  - Pharyngeal diverticula
- Use of medications that alter swallowing function
  - Benztropine mesylate (Cogentin)
  - Oxybutynin (Ditropan)

- Propantheline (Pro-Banthine)
- Tolterodine (Detrol)
- The presence of tracheostomy tube.
- Nasal obstruction.

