**Plans for Data Analysis:**

- The data collected will include swallow frequency (calculated as swallows per minute), peak effort amplitude (the highest amplitude of swallowing effort), and swallowing speed (the difference between the onset and offset of muscle contraction). Simple 1-way repeated measures ANOVA will be used to determine significant differences in swallowing frequency between oxygen flow rates ( $p < .05$ ). A 4-way mixed methods repeated measures ANOVA (HFNC x volume x viscosity x age) will be used to determine significant differences in amplitude and timing ( $p < .05$ ).

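### Sex is named as an influence on swallow amplitude and timing but is neither balanced across the age groups nor modelled, so the age effect on these outcomes can partly reflect sex

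*Combined protocol and SAP*

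**What the plan says.** Under Swallowing Effort and Timing, the protocol states: "Prior research has shown that both amplitude and timing are influenced by multiple factors". It lists bolus volume and viscosity, "and the age and gender of the person swallowing".

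Experimental Design and methods sets the enrolment by age alone: "25 participants will be between 21 and 49 years old; and the other 25 above 50 years old". The stated purpose of the split is to "determine if there are any swallowing differences between the different age groups". Recruitment starts with an email to "faculty, students and employees in the departments of Respiratory Care and Speech Language Pathology", and then: "Snowball sampling (non-probability sampling) will also be utilized to recruit individuals outside of those departments".

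Subject Population repeats the total ("Fifty healthy adult volunteers above the age of 21 will be assessed") and contains no criterion or target for sex.

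Plans for Data Analysis gives the model: "A 4-way mixed methods repeated measures ANOVA (HFNC x volume x viscosity x age) will be used to determine significant differences in amplitude and timing". Swallowing frequency is analysed separately, by a one-way repeated measures ANOVA on flow rate only. Gender is not mentioned again after the introduction.

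**The concern.** The protocol names four influences on amplitude and timing. Three are handled: volume and viscosity are varied within each person, age has a 25/25 quota, and all three are model factors. The fourth, gender, is left out of enrolment and out of the analysis.

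This matters for age because age group cannot be randomised. Its main effect can be read as an age effect only if the two groups are alike in other known influences, or if the model adjusts for them. A non-probability sample with no sex target does not secure the first, and the stated ANOVA does not provide the second. If the sex mix differs between the groups, part of any sex effect is counted as an age effect. It could create an apparent age difference or mask a real one. The HFNC x age term is exposed in the same way, but only if men and women respond differently to flow.

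**Working it through.** **Figure to reproduce.** None. The plan gives no effect size, SD, power or sample-size derivation.

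**Inputs from the documents.** 25 participants per age group; age as a between-person factor; significance level 0.05 (taken as two-sided, since the plan does not say).

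**Assumed inputs.** The number of women in each group, and the sex effect in units of the within-sex SD of participant means. The documents give neither, so a range is shown.

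**Step 1: which contrasts are exposed.** Every participant has the baseline, all three flows and all bolus types. Sex is constant within a person, so it cancels from the flow, volume and viscosity contrasts. It does not cancel from the age contrast. The frequency ANOVA has no age term, so no age comparison is planned there.

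**Step 2: bias in the age contrast.** Bias = sex effect x difference in the share of women.

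- 20 vs 12 women: difference = 8/25 = 0.32. Bias = 0.3 x 0.32 = 0.096 SD, 0.5 x 0.32 = 0.16 SD, 0.8 x 0.32 = 0.256 SD.
- 22 vs 10 women: 12/25 = 0.48. Bias = 0.8 x 0.48 = 0.384 SD.
- 15 vs 10 women: 5/25 = 0.20. Bias = 0.8 x 0.20 = 0.16 SD.

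For scale, the age difference detectable with 80% power is about (1.960 + 0.842) x sqrt(2/25) = 0.79 SD.

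**Step 3: false-positive rate of the unadjusted age test.** Two-sample t-test on participant means, 48 df, no true age effect, 100,000 simulated trials per case. The sex-related spread within each group is left in the error term, as it would be in the planned analysis.

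| Women per 25 (one group vs the other) | Sex effect (SD) | Rejection rate at nominal 5% |
|---|---|---|
| 20 vs 12 | 0.3 | 6.0% |
| 20 vs 12 | 0.5 | 7.6% |
| 20 vs 12 | 0.8 | 11.5% |
| 22 vs 10 | 0.8 | 23% |
| 15 vs 10 | 0.8 | 6.5% |

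A repeat with 400,000 trials agreed to within about 0.2 percentage points.

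**Step 4: cost of adjusting for sex.** Error df for the age effect fall from 50 - 2 = 48 to 50 - 3 = 47. The variance of the age contrast is multiplied by 1/(1 - r²), where r is the correlation of age group with sex. For two equal groups, r² = (difference in share)² x 0.25 / [p(1 - p)], with p the overall share of women.

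- 20 vs 12: p = 32/50 = 0.64; r² = 0.1024 x 0.25 / 0.2304 = 0.111; factor 1.13.
- 22 vs 10: p = 0.64; r² = 0.2304 x 0.25 / 0.2304 = 0.25; factor 1.33.
- Equal split: r² = 0; factor 1.00.

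**The case against.** The strongest reply is that this is a study of flow rate. The Specific Aims do not mention age, and each participant serves as their own control for flow. That stands: a reader might infer that the flow findings are confounded by sex, and the design rules this out.

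Four further points on the other side also stand.

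- A reader might infer that age and sex could never be disentangled once the data are in. If sex is known, adding it to the model separates them unless the two coincide completely. Nor do the documents show that sex will go unrecorded: the list of data in Plans for Data Analysis covers outcomes only and omits age as well, although age is in the model. What the documents support is that no adjustment is pre-specified.
- It is tempting to suppose that older participants will arrive mainly by referral and younger ones by email. The email goes to faculty and employees as well as students, and referral is meant for people outside the departments. No text ties recruitment route to age or to sex.
- Chance imbalance is not evidence of an inflated error rate. With 50% women expected in both groups, a gap of 5 or more women arises in about 20% of samples, yet the unconditional rejection rate stays at about 5%. The concern is a systematic difference in sex mix, which the recruitment does nothing to prevent.
- All sizes rest on assumed mixes and effects, and mild imbalance does little harm.

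The omission itself remains. The protocol identifies the influence, plans the comparison that it can distort, and provides for it in neither enrolment nor analysis.

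**Conclusion.** The point holds for the age main effect on amplitude and timing, and for HFNC x age if sex modifies the response to flow. It goes no further: the within-person contrasts, the primary aim and the frequency analysis are unaffected.

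That the plan leaves sex out is certain from the text. How much it matters is not known. Under the assumed cases the false-positive rate of the age test runs from near nominal (about 6.5% at 15 vs 10 women with a 0.8 SD effect) to about 23% (22 vs 10 with the same effect). These figures assume a two-sided test on participant means and a sex effect of the same size in both age groups. The change is worth making because it is cheap and removes the ambiguity from a comparison that the protocol says it wants to make.

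**What to change.** 1. Record sex at enrolment and tabulate it by age group.
2. In Plans for Data Analysis, add sex as a between-subject term in the amplitude and timing model, and report the sex-adjusted age effect as the age result.
3. Include sex x HFNC whenever HFNC x age is interpreted. A sex main effect alone does not protect that interaction.
4. In Experimental Design and methods and in Subject Population, state the aim of a similar female-to-male split in the two age groups where recruitment allows. A target is enough. A strict quota of 12 to 13 of each sex per group would be hard to justify in an unpaid convenience sample.

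Cost: no extra participants or procedures, and one variable to record. The main effect uses one degree of freedom and sex x HFNC a few more (3 if baseline and three flows are the levels, 2 if only the flows). If the groups are unbalanced, the interval for the age contrast widens somewhat: the variance factors of 1.13 and 1.33 correspond to intervals about 6% and 15% wider (square roots 1.06 and 1.15). Working towards a similar split may slow recruitment a little.

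### Flow order is randomised but the planned ANOVAs have no period term, so any drift across the session is left in the error of the flow comparison and costs precision

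*Combined protocol and SAP*

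**What the plan says.** Under Experimental Design and methods, the sample is "fifty healthy adult volunteers (25 participants will be between 21 and 49 years old; and the other 25 above 50 years old"). Every session opens with the no-flow condition: "each participant will sit quietly for 10 minutes, before being attached to the HFNC, so a baseline swallow frequency can be established". Eight baseline boluses follow, and then: "Once these swallows have been completed, the participant will be placed on the HFNC".

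The flows are a three-period crossover: "Each participant will be placed on three different flow rates (30, 45, and 60 L/min or 30, 45, and 50 L/min) in random order". The only statement on how the sequence is produced is "The random order will be generated by an online random number tool". No blocks, Latin square, sequence quota or stratification by age is mentioned. On timing, "The study participant will be subjected to each flow rate for 15 minutes", and after each flow's boluses "the participant will be removed from the HFNC for a period of 10 minutes".

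Plans for Data Analysis names the factors of each model. For frequency: "Simple 1-way repeated measures ANOVA will be used to determine significant differences in swallowing frequency between oxygen flow rates". For amplitude and timing it names a four-way mixed ANOVA with HFNC, volume, viscosity and age. Period, order and sequence appear in neither model.

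**The concern.** The three periods are not alike in the schedule. Frequency in the first flow period is recorded straight after the eight baseline boluses. In the second and third it is recorded after a 10-minute rest off the device. Each later period also comes with more session time, more boluses already swallowed (32 by the end) and earlier HFNC exposure. If any of this shifts swallowing, measurements differ by period whatever the flow.

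A crossover analysis normally takes such differences out with a period term. Without one they stay in the within-person variation against which flow is tested. The documents give no sample-size calculation, so no spare power has been shown that could absorb the loss.

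**Working it through.** The plan states no power, effect size or SD, so there is no figure of its own to reproduce.

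**Inputs from the documents:** n = 50 (25 per age group), three flows per person, order randomised, alpha 0.05, no period term.

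**Assumptions, not in the documents:** independent within-person errors with SD 1; flow means −0.3, 0 and +0.3 (0.6 SD from lowest to highest flow); linear drift of d SD per period.

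**1. Error inflation.** With freely randomised order and no period term, the expected residual mean square is σ² + S², where S² is the variance of the three period effects. For effects −d, 0, +d, S² = (d² + 0 + d²)/2 = d². With σ = 1 the residual is therefore multiplied by 1 + d².

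**2. Power as planned.** The omnibus F test has 2 and 2 × 49 = 98 df and a critical value of 3.09. Its noncentrality is λ = 50 × (0.3² + 0 + 0.3²)/(1 + d²) = 9/(1 + d²).

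| d (SD per period) | 1 + d² | λ | Power, noncentral F | Power, simulated | n that offsets it, 50(1 + d²) |
|---|---|---|---|---|---|
| 0 | 1.00 | 9.00 | 76% | 75–76% | 50 |
| 0.25 | 1.06 | 8.47 | 73% | 73% | 53.1 |
| 0.5 | 1.25 | 7.20 | 65% | 65–68% | 62.5 |
| 0.75 | 1.56 | 5.76 | 55% | 54–56% | 78.1 |

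Balanced order with a period term (2 and 96 df) gives about 75 to 77% in every row.

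**3. Type I error as planned.** Under the null, the flow mean square has the same expectation, σ² + d², as the residual. The test therefore keeps its level: simulated rejection was about 5% at every drift examined.

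**4. Which change does the work, at d = 0.5.**

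| | No period term | Period term |
|---|---|---|
| Free order | 65–68% | 75–77% |
| Balanced order | 65% | 76–77% |

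The period term recovers nearly all the loss. Balancing alone recovers none. It also removes drift from the flow mean square but not from the residual, so the test becomes conservative: type I error is about 2.5% at d = 0.5 and about 1% at d = 0.75.

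**5. Chance imbalance.** For one person, two flows are one period apart with probability 2/3 and two apart with probability 1/3. The variance of the signed difference is 2/3 × 1 + 1/3 × 4 = 2. Averaged over 50 people under free order, its SD is √(2/50) = 0.20 periods. If 48 people are in complete blocks and two are left over, it is √(2 × 2)/50 = 0.04. At d = 0.5 that is a random shift of 0.10 SD in the contrast between two flows, against 0.02.

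**The case against.** The strongest reply is that the plan as written is valid. Order is randomised for each participant, so flow contrasts are unbiased on average and the flow test holds its level. That stands. A reader might infer bias or a distorted type I error, and the documents do not support either. The rates of 2.5% and 1% belong to balanced order without a period term, a design the protocol does not describe.

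A reader might also blame the randomisation method. Under free order, a group of 25 has a 6% chance that one of the six sequences is never used and a 62% chance that sequence counts differ by 5 or more. These figures look striking but hardly touch power, as step 4 shows. That the order is unrestricted is also inferred from silence: a balanced list could be made with the same tool. The missing period term does not depend on that inference.

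Third, the schedule does not prove drift. It shows that the first flow period lacks a preceding rest, not that swallowing changes as a result, and the 10-minute rests may limit drift or carry-over. At 0.25 SD per period the loss is only 2 to 3 points. Losses of 10 points or more need a total drift of about 1 SD from the first to the third period.

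Last, the calculation covers a three-level test on a single measure. The four-way model, with eight swallows per condition, was not simulated, so the power figures do not carry over to amplitude and timing. The mechanism does.

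**Conclusion.** The point holds as one of efficiency. Both planned models omit period, so any drift in the session inflates the error of the flow comparison. Under the stated assumptions the loss is nil without drift, 2 to 3 points of power at 0.25 SD per period, roughly 10 at 0.5 and roughly 20 at 0.75. The true drift, the within-person SD and the flow effect are all unknown from the documents. The result is neither biased on average nor invalid. Because the remedy is standard and nearly free, the change lies between worth considering and recommended.

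**What to change.** For the three randomised flows, analyse frequency, amplitude and timing with a crossover linear mixed model: participant random, flow and period fixed, plus volume, viscosity and age where already planned. For amplitude and timing, add a random participant-by-period term, because the eight swallows in one period are not independent replicates of the flow. Period cannot simply be crossed with flow as a further factor in a conventional repeated-measures ANOVA, since each person fills only 3 of the 9 flow-by-period cells.

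Report the contrast with the no-flow baseline separately. Baseline always comes first, so no model can separate it from period. The plan does not say whether baseline is a level of the ANOVA, and it should.

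As a secondary step, use the same tool before enrolment to produce permuted blocks of the six sequences within each age group. With 25 = 4 × 6 + 1 exact balance is impossible, but near balance limits chance imbalance and may add a few points of power. Do this only together with the period term.

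The cost is 2 df, a mixed model in place of a simple ANOVA, and at most a few points of power if there is no drift. No extra participants or procedures are needed.
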